#### Johns Hopkins Medicine - eForm A

- Use the section headings to write the eForm A, inserting the appropriate material in each. If a section is not applicable, leave heading in and insert N/A.
- When submitting eForm A (new or revised), enter the date submitted to the field at the top of eForm A.

#### 1. Abstract

a. Provide no more than a one page research abstract briefly stating the problem, the research hypothesis, and the importance of the research.

One of the most promising lines of investigation for the therapeutic use of hallucinogens in the 1960s and 1970s was in the treatment of drug dependence. However, these studies did not involve the rigor and controls expected of modern clinical psychopharmacology research, making the efficacy of this approach difficult to judge. We propose to examine psilocybin administration combined with a structured smoking cessation program in nicotine dependent individuals to provide preliminary data on the efficacy of this combined treatment in smoking cessation. Prior work in our laboratory has shown that under carefully prepared and supportive conditions, psilocybin administration can facilitate highly salient experiences with enduring personal meaning and spiritual significance (Griffiths et al., 2006, 2008, 2011). It is plausible that embedding such highly meaningful experiences into a drug dependence cessation attempt may provide an enduring motivation for remaining abstinent. Cigarette smoking is a good model system for studying drug dependence because users are less likely to be challenged by the many social and economic impairments that often accompany dependence on other drugs such as cocaine, heroin, or alcohol. More specifically, we propose to conduct a pilot study in which psilocybin is administered under highly supportive conditions to individuals who are nicotinedependent cigarette smokers, who have had multiple unsuccessful quit attempts, and who continue to desire to quit smoking. Other than nicotine dependence, participants will be healthy.

In total, 115 participants will complete this pilot study. Fifteen individuals have already undergone the initially approved protocol with no clinically significant adverse events. A further 100 participants will be randomized to a psilocybin condition or a nicotine replacement therapy (NRT; i.e., transdermal nicotine patch) condition, 60 of whom will be studied with functional neuroimaging procedures. The NRT condition will serve as an important control for evaluating relative efficacy of the psilocybin condition, as well as examining differences in neuroimaging results. After screening and enrollment, individuals who are eligible for MRI scanning (n=60) will be invited to complete an optional preliminary sub-study protocol consisting of a 6-8 hour MRI scan, blood draw, and questionnaire assessment at the National Institute on Drug Abuse (NIDA) Intramural Research Program on the Johns Hopkins Bayview Campus. After completing the sub-study protocol, or opting out, participants will begin a 13-week cognitive-behavioral smoking cessation intervention, with Target Quit Date (TQD) set in approximately week 5. Participants who are eligible for and willing to participate in MRI scanning (n=60), will have MRI scans conducted in weeks 2 and 5, and at 3-month follow-up for those participants who have maintained smoking abstinence to that point. Individuals who do not meet MRI scanning inclusion criteria, but are otherwise eligible to enroll (n=40), will complete only the treatmentrelated portions of the study.

During the third treatment meeting in week 3, participants will be randomized into one of two treatment conditions (i.e., psilocybin or NRT). In one condition a single high-dose

(30mg/70kg) of psilocybin will be administered in the context of a 13-week smoking cessation treatment protocol. In the other condition an 8 to 10 week regimen of NRT (patch) will be administered within the same 13-week treatment protocol. Participants in both conditions will meet weekly with study staff during weeks 1-7, and at two-week intervals during weeks 8-13 (i.e., in weeks 9, 11, and 13) of the 13-week treatment period. All participants will be asked to complete follow-up meetings at 3, 6, and 12 months post-TQD to assess smoking status and complete questionnaires. Additionally, in order to prevent differential dropout driven by individuals who hope to receive the novel psilocybin treatment, participants randomized to the NRT condition will be offered an optional psilocybin (30 mg/70 kg) session after completing their 6-month follow-up.

A number of measures that assess the psychological process of smoking cessation will be utilized at intake and repeatedly after the psilocybin session or initiation of NRT. In order to explore the contribution of spiritual experience to smoking cessation success in the psilocybin treatment condition, questionnaires that assess the spiritual nature of the psilocybin session experiences will be given after the psilocybin session. In order to assess the hypothesis that spiritual experience or smoking cessation is associated with changes in immune function or stress hormones, blood samples at baseline and 1-week post-TQD will be collected from both groups for cytokine and hormonal analyses when possible. Diurnal saliva samples of cortisol will also be assessed at baseline, and 1-week post-TQD. In order to examine neural mechanisms associated with psilocybin-facilitated smoking cessation, MRI data will be compared withinsubjects and between treatment groups in a subset of up to 60 participants who complete MRI scanning procedures.

#### 2. Objectives (include all primary and secondary objectives)

**Primary objective:** This is a pilot study to provide preliminary evidence on the efficacy of psilocybin administration combined with a structured smoking cessation program for the treatment of nicotine dependence. In order to differentiate the role of psilocybin from the role of cognitive-behavioral therapy and support from study staff, a randomized control group will be utilized. Participants in the control condition will receive a matched cognitive-behavioral intervention in conjunction with NRT. The results should also provide information about clinical trends that may be compared with previously published smoking cessation research that utilized cognitive-behavioral therapy or NRT (e.g., Fiore et al., 1994; Stapleton et al., 2013; Sykes & Marks, 2004). Such trends will indicate whether a larger-scale, rigorously controlled experimental study is warranted.

**Secondary objective:** In addition to providing preliminary information on efficacy, the proposed pilot study will also provide valuable clinical experience for us to continue developing a psilocybin-based clinical intervention for treatment of drug dependence (e.g., smoking cessation). Such clinical experience will consist of both qualitative data from participant interviews and a battery of quantitative outcome measures, most of which are well-validated instruments with demonstrated clinical relevance. These measures will provide data that indicate which factors are theoretically relevant to the proposed intervention, and may assist in the design of further controlled trials if follow up investigation is warranted. In addition to the assessment of mystical-type experience (implicated as important to the attribution of behavioral change in previous research; Garcia-Romeu et al., 2015; Griffiths et al., 2006), relevant factors to be studied include self-efficacy, personal values, temporal perspective, and mood, (which are known to relate to nicotine dependence or smoking cessation). Outcome measures also include blood and saliva hormonal markers of stress. Blood samples will additionally allow for the

assessment of cytokine markers of immune function, which will provide an opportunity to examine the hypothesized link between mystical-type experience and improved immune function (Roberts, 2006). Finally, the collection of MRI data will allow for a preliminary examination of underlying neural mechanisms that may play a role in psilocybin-facilitated smoking cessation, including the intermediate and persisting effects of psilocybin on resting state functional connectivity, and potential brain-based factors that may be useful predictors or mediators of treatment outcome.

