Potential participants will be carefully screened to eliminate those with significant medical or psychiatric illnesses. Evaluation will include a history and physical examination, CBC, SMA-24 (or equivalent), ECG, and urine drug test. Participants will also be requested to refrain from illicit drug use during the course of the study and a urine test will be conducted before the administration of psilocybin. Left-handed individuals are ineligible for MRI scanning, but may otherwise complete the study treatment. Pregnant or nursing women are ineligible; female participants will receive a urine pregnancy test at intake and before psilocybin administration, and must use effective methods of contraception during the study. Other medical exclusion criteria are presented in section 5. With regard to psychiatric screening, based on clinical interviews and a structured psychiatric diagnostic interview, participants will be eligible if they are judged to be psychologically stable and do not meet any of the psychiatric exclusion criteria (as defined by DSM-IV) presented in section 5. Psychiatric screening interviews may take place remotely via secure online platform.

Meetings Before and After TOD (Psilocybin Condition): Before the psilocybin session day participants in the psilocybin condition will meet with one or more of the study staff on at least 3 occasions, for a minimum of 4 hours of contact time before the session day. Some flexibility in scheduling will be allowed to account for unexpected absences such as travel commitments or illnesses. The main purpose of the participant-staff meetings is to develop rapport and trust, which we believe helps minimize the risk of fear or anxiety reactions during the psilocybin session. Additional meetings and contact hours (up to 10 hours) will be scheduled if it is judged necessary to establish rapport and trust. The participant's life history and current situation in life will be reviewed.

Timeline a	Psilocybin condition meetings (duration)	NRT condition meetings (duration)
	Screening Day 1/ C	Consent (6 hrs)
	Screening Day 2 (2-3 hrs)	
-	Optional NIDA sub-study protocol / MRI Scan 1 (6-8 hrs)*	
	MRI task training at NIDA (2-3 hrs)*	
	Treatment meeting 1 (1-2 hrs)	
Week 1	Study orientation	
	Assign Target Quit	Date (TQD)
	Sign contract to quit / smoking diary introduction	
	MRI scan 2 (4-5 hrs)*	
	Treatment meeting 2 (1-2 hrs) Carbon monoxide demonstration	
Week 2		

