	Smoking financial costs	
	Identifying motivation to quit	
	Treatment meeting 3 (90 min)	Treatment meeting 3 (90 min)
	Randomization to treatment condition	Randomization to treatment condition
Week 3	Discuss previous quit attempts	Discuss previous quit attempts
	Weight gain and quitting smoking	Weight gain and quitting smoking
	Recovery symptoms	Recovery symptoms
	Discussing psilocybin effects	Discussing NRT effects
	Treatment meeting 4 (90 min)	Treatment meeting 4 (90 min)
	Smoking diary discussion	Smoking diary discussion
Week 4	Dealing with urges after TQD	Dealing with urges after TQD
	Preparing to quit	Preparing to quit
	What to expect in psilocybin session	How to take NRT
	Psilocybin session / TQD (8 hrs)	MRI scan 3 / TQD (4-6 hrs)*
Week 5	MRI scan 3 (4-6 hrs; Next day)*	Treatment meeting 5 (1-2 hrs)
	Treatment meeting 5 (1-2 hrs; Next day)	Initiation of NRT
	Participant Narrative of Session	
	Treatment meeting 6 (45 min)	Treatment meeting 6 / TQD (45 min)
Week 6	Identifying triggers	Identifying triggers
	Overcoming urges to smoke	Overcoming urges to smoke
	Treatment meeting 7 (45 min)	Treatment meeting 7 (45 min)
Week 7	Supporting smoking abstinence	Supporting smoking abstinence
	Treatment meeting 8 (45 min)	Treatment meeting 8 (45 min)
Week 9	Supporting smoking abstinence	Supporting smoking abstinence
	Treatment meeting 9 (45 min)	Treatment meeting 9 (45 min)
Week 11	Supporting smoking abstinence	Supporting smoking abstinence
W. 1.10	Treatment meeting 10 (45 min)	Treatment meeting 10 (45 min)
Week 13	Clinical interview	Clinical interview
3 months post-TQD	Follow-up meeting (2-4 hrs)	Follow-up meeting (2-4 hrs)
	MKI Scan 4 ° (4-6 hours)*	MRI Scan 4° (4-6 hours)*
6 months post-TQD	Follow-up meeting (2-4 hrs)	Follow-up meeting (2-4 hrs)
12 months post-TOD	Follow-up meeting (2-4 hrs)	Follow-up meeting (2-4 hrs)

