#### 5. Drugs/ Substances/ Devices

#### a. The rationale for choosing the drug and dose or for choosing the device to be used.

**Psilocybin dose:** On the drug session day, participants will be administered 30mg/70kg psilocybin. Two previous studies in our laboratory on psilocybin suggest that this dose is associated with mystical-type experiences, with some variability across participants (Griffiths et al., 2006; Griffiths et al., 2011). This dose has been safely administered in our laboratory (Griffiths et al., 2006; Griffiths et al., 2011), is in the range of doses examined extensively in previous studies with hallucinogen-naïve individuals (Malitz et al. 1960 Metzner et al. 1965; Pahnke 1963, 1969; Pahnke et al. 1966; Leuner 1981), and is less than that (49mg/70kg) administered safely under a previously authorized IND (Strassman 1992, 1998). Furthermore, to attenuate the possibility of a non-optimal response in individuals with higher body weight, this study will use an absolute maximum dosage of 50 mg, which is approximately equivalent to absolute doses we have administered safely to heavier participants in previous studies with psilocybin.

**Transdermal nicotine patch dose:** Nicotine replacement therapy (NRT) is widely considered a first-line smoking cessation treatment option that is available over the counter (Silagy et al., 2000; Stead et al., 2012). As such, it was chosen to provide a proven control treatment with known efficacy. NRT patch doses will be administered according to recommended label usage. For individuals who smoke more than 10 cigarettes per day: 21mg daily for weeks 1-6, 14mg daily for weeks 7-8, 7mg daily for weeks 9-10; for individuals who smoke 10 or less cigarettes per day: 14mg daily for weeks 1-6, 7mg daily for weeks 7-8 (FDA label, PDR.net). Patch use will begin in week 5 of treatment, after 24-hours of smoking abstinence.

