#### c. Statistical plan including sample size justification and interim data analysis.

This is a pilot comparative efficacy study with a randomized control condition. Demographics and smoking history at baseline will be examined for between group differences using Fisher's exact tests and independent-samples t-tests. The primary outcome variable will be a between group comparison of the percent of volunteers who show biologically verified (via carbon monoxide and cotinine measures) and self-reported smoking abstinence post-TQD, allowing for a grace period for initiation of prolonged abstinence within 14 days after the target-quit date in line with current recommendations for best practices in smoking cessation clinical trials (Piper et al., 2020). For this primary analysis, positive cotinine samples will be counted as smoking abstinent if the person indicates on the TLFB that they have used non-smoking forms of nicotine. This comparison will be performed using a logistic regression analysis, with treatment condition

as the predictor variable and prolonged abstinence as the examined outcome. Although the study sample will be small, these results will provide useful preliminary data indicating whether follow up investigation in this area is warranted. Between groups comparisons of secondary measures will examine differences across treatment conditions on variables such as smoking urges and withdrawal using independent-samples t-tests. We will apply a 2-step approach when assessing between-group differences in these variables. First, we will compare values between all participants still enrolled in the study at 6-months post-TQD, then only among those still smoking at 6 months post-TQD according to 7-day point prevalence criteria. In order to rule out the role of alternative sources of nicotine in achieving smoking abstinence, we will perform a secondary analysis where participants who stopped smoking tobacco cigarettes and initiated alternative forms of nicotine use (e.g., e-cigarettes, smokeless tobacco) will be coded as non-abstinent.

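### The primary objective says the control arm will separate psilocybin from staff support, but only the psilocybin arm has an 8-hour staffed session and the control takes an active drug, so the trial compares two packages

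*Combined protocol and SAP*

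**What the plan says.** Section 2 (Objectives), under the primary objective, gives the reason for having a randomised control: "In order to differentiate the role of psilocybin from the role of cognitive-behavioral therapy and support from study staff". The next sentence defines the control: "Participants in the control condition will receive a matched cognitive-behavioral intervention in conjunction with NRT".

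Other sections describe what each arm receives.

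- The timeline table in section 3.a lists ten treatment meetings of equal length in both arms. In week 5 it adds, for the psilocybin arm only, "Psilocybin session / TQD (8 hrs").
- Section 3.a, on the conduct of the session, keeps staff in the room throughout, for at least 7 hours, to attend to physical and emotional needs. It expects sessions to last 7 to 10 hours.
- The section 3.a text on meetings in the psilocybin condition allows extra rapport-building contact before the session (up to 10 hours). After the session it allows further hours to discuss the experience or to support abstinence. The parallel text for the NRT condition has neither provision.
- Section 5.a says of the patch that "it was chosen to provide a proven control treatment with known efficacy".
- Section 3.c rules out blinding, and section 3.e says there is no placebo or non-treatment group.
- Section 6.c states: "This is a pilot comparative efficacy study with a randomized control condition". The primary model is a logistic regression with treatment condition as the predictor.

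**The concern.** The objective gives the randomised contrast a job of attribution: to tell the part played by psilocybin from the parts played by CBT and by staff support. For that, the arms would have to be alike in CBT and in staff support and differ only in psilocybin. They are alike in scheduled CBT. They differ in staff support, in the second drug (patch or none) and, because treatment is open-label, in what participants expect.

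The stake is how the result is read. A reader who takes section 2 at its word would credit a positive result to psilocybin itself, although prolonged staff presence came with it. The same reader could take a null result to mean that psilocybin contributes nothing, although the comparator is an effective treatment. Section 2 says the trends will inform whether a larger, rigorously controlled trial is warranted, so the attribution has consequences even in a pilot.

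**Working it through.** **1. The plan's own contact figure.** The documents give no contact hours by arm. Section 3.b gives meeting counts: 11 in the treatment phase and about 16–22 in total. From the timeline: 2 screening + 11 treatment + 3 follow-up = 16, and with the 6 optional meetings, 22. This reproduces the figure. The 11 fits the psilocybin arm (10 meetings + the session). The NRT arm has 10 by the table, giving 15 or 21, which is close enough for an approximate statement.

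**2. Scheduled treatment contact, from the section 3.a table.**

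| Item | NRT arm | Psilocybin arm |
|---|---|---|
| Meetings 1, 2 and 5 (1–2 h each) | 3–6 h | 3–6 h |
| Meetings 3 and 4 (1.5 h each) | 3 h | 3 h |
| Meetings 6–10 (5 × 0.75 h) | 3.75 h | 3.75 h |
| Psilocybin session | none | 8 h |
| Total | 9.75–12.75 h | 17.75–20.75 h |

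Without the session the ratio is exactly 1.0. With it, 17.75 / 9.75 = 1.82 at the short durations and 20.75 / 12.75 = 1.63 at the long ones.

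**3. How far the ratio depends on what is counted.**

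- Session of 7 to 10 h instead of 8: from 19.75 / 12.75 = 1.55 to 19.75 / 9.75 = 2.03.
- Screening (8–9 h) and three follow-ups (2–4 h each) added to both arms: 31.75 / 23.75 = 1.34 and 41.75 / 33.75 = 1.24.
- MRI participants, counting the week 2 and week 5 scans (8–11 h in both arms, with a staff member present): 25.75 / 17.75 = 1.45 and 31.75 / 23.75 = 1.34. The Abstract puts 60 of the 100 randomised participants in this group.
- Full use of the extra preparation allowed in the psilocybin arm, if the 10 h come on top of the schedule: 27.75 / 9.75 = 2.85 and 30.75 / 12.75 = 2.41. If 10 h is instead the ceiling for all contact before the session (5–7 h are already scheduled), 22.75 / 9.75 = 2.33 and 23.75 / 12.75 = 1.86.

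The ratio moves with the basis. The scheduled excess of 8 h in the psilocybin arm does not.

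**4. What the two-arm contrast estimates.** On the log-odds scale, and assuming additive components, let c be the CBT and support common to both arms, p psilocybin, s the staff support in the session, and n the patch.

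- Psilocybin arm: c + p + s
- NRT arm: c + n
- Difference: p + s − n

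Two arms give two equations for four unknowns. The common term c cancels, which is what matched CBT achieves. Of the effects of interest, only the combination p + s − n is estimable. Neither p alone nor p + s (the psilocybin package added to CBT without a patch) can be recovered. Open-label treatment adds a difference in expectancy to the same sum.

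**5. Whether the analysis repairs this.** The primary model in section 6.c states no term for contact or expectancy. Adding contact time would not help: it follows randomisation and is largely fixed by arm. Section 6.b collects the pre-session expectation rating in the psilocybin condition only, so that rating cannot support a comparison between arms.

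**The case against.** The strongest reply is that the objective is met where it matters most. CBT is matched: meeting lengths are equal, section 3.a calls the NRT arm's programme identical, both arms have the same minimum of three meetings and four hours before treatment, and telephone support after the quit date is the same. A reader might infer from the contact totals that the psilocybin arm receives more CBT. The documents do not support that, because the whole scheduled excess is the drug session, where the participant lies with eyeshades and music. This part of the reply stands in full.

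The second reply is that the supervised session is simply how the drug is given, and that hours of supervision should not be weighed like hours of counselling. The weighting point stands: nothing in the documents equates the two, and the hours are not a measure of therapeutic dose. But section 3.a says the session is meant to strengthen motivation to quit, and section 7.b counts the monitors' presence as reassurance resting on trust built beforehand. That is staff support, and one arm receives it. If the session belongs to the intervention, the objective should say so and not claim to separate the two.

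The third reply is that an active control is conservative and openly justified. If the patch does not reduce abstinence (n ≥ 0), a positive p + s − n implies a positive p + s, so the package would also beat CBT alone under the additive model, expectancy aside. This stands for a positive result. It does not separate p from s, and it does not help with a null, where p + s = n could still be a real benefit.

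Finally, the study is a pilot seeking preliminary evidence. That limits precision and the strength of conclusions, but not which effect the contrast estimates.

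**Conclusion.** The concern holds for staff support and for the missing CBT-only reference; it does not hold for scheduled CBT. The randomised comparison estimates psilocybin with its supported session and CBT against NRT with CBT. The imbalance is 8 scheduled hours: 17.75–20.75 h against 9.75–12.75 h, a ratio of 1.63–1.82 for treatment meetings plus the session, and about 1.24–1.34 once screening and all follow-ups are counted. The hours assume the approximate durations in the timeline and none of the discretionary contact, which is written for the psilocybin arm only.

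Two stronger readings should be resisted. A reader might take 1.6–1.8 as the ratio for all study contact; it holds only on the basis named. A reader might also infer that the trial cannot support any useful comparison. It can: the contrast between packages is a legitimate estimate of relative efficacy, which is how the Abstract describes the purpose of the NRT arm. The fault lies in what section 2 says the contrast will show. Correcting it changes no endpoint, model or sample size, but it changes what the trial may conclude, so it should be done.

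**What to change.** 1. Restate the primary objective in section 2, in line with the Abstract. Suggested text: *To provide preliminary evidence on the efficacy of psilocybin-assisted CBT, including the supported psilocybin session, relative to NRT-assisted CBT. Scheduled CBT meetings are the same in both arms. The comparison does not separate psilocybin from the staff support given with it, and does not estimate the effect of psilocybin added to CBT alone.* Section 6.c calls the study comparative but does not describe the packages, so it could carry the same wording.
2. Remove the claim to differentiate psilocybin from staff support.
3. Report staff-contact time by arm with the primary result, split into scheduled treatment meetings, the psilocybin session, and discretionary extra contact. Use it descriptively and not as a covariate.

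The cost is a change of wording and a tabulation, which should be obtainable from visit records. Treatment, visits, sample size and the primary model stay as they are. The drawback is a less ambitious claim: the effect of the drug apart from its session would be left to a later trial.
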